3.2. Exclusion Criteria

Patients eligible for this study *must not* meet any of the following criteria:

1. Patient received prior treatment with any CDK4/6 inhibitor
2. Patient has a known hypersensitivity to any of the excipients of ribociclib.
3. Patients with a prior malignancy diagnosed within 2 years AND with evidence of disease (except adequately treated, basal or squamous cell carcinoma, non-melanomatous skin cancer or curatively resected cervical cancer)
4. Patient with concurrent malignancy that is not clinically stable AND needs tumor-directed therapy.
5. Patients with central nervous system (CNS) involvement unless they meet ALL the following criteria:
 - a. Untreated brain metastases (e.g., lesions < 1cm) not needing immediate local therapy.
 - b. Previously treated brain metastases not needing immediate local therapy.
 - At least 4 weeks from prior therapy completion (including radiation and/or surgery) to starting the study treatment.
 - Clinically stable CNS tumor at the time of screening and not receiving steroids and/or enzyme-inducing anti-epileptic medications for brain metastases.
6. Clinically significant, uncontrolled heart disease and/or cardiac repolarization abnormalities, including any of the following:
 - a. History of acute coronary syndromes (including myocardial infarction, unstable angina, coronary artery bypass grafting, coronary angioplasty, or stenting) or symptomatic pericarditis within 6 months prior to screening.
 - b. Documented cardiomyopathy.
 - c. Clinically significant cardiac arrhythmias (e.g. ventricular tachycardia), complete left bundle branch block, high-grade AV block (e.g. bifascicular block, Mobitz type II and third-degree AV block).
 - d. Long QT syndrome or family history of idiopathic sudden death or congenital long QT syndrome, or any of the following:
 - Risk factors for Torsades de Pointe (TdP) including uncorrected hypokalemia or hypomagnesemia, history of cardiac failure, or history of clinically significant/symptomatic bradycardia.
 - Concomitant use of medication(s) with a known risk to prolong the QT interval and/or known to cause Torsades de Pointe that cannot be discontinued (within 5 half-lives or 7 days prior to starting study drug) or replaced by safe alternative medication.
 - Inability to determine the QT interval on screening (QTcF, using Fridericia's correction).
 - e. Systolic blood pressure (SBP) >160 mmHg or <90 mmHg at screening.
7. Patient is currently receiving any of the following medications and cannot be discontinued 7 days prior to starting study drug (see Table 1 for details):
 - a. Known strong inducers or inhibitors of CYP3A4/5, including grapefruit, grapefruit hybrids, pummelos, star-fruit, and Seville oranges.

- b. That have a narrow therapeutic window and are predominantly metabolized through CYP3A4/5.
- c. Herbal preparations/medications, dietary supplements.
- d. Warfarin or other coumadin-derived anticoagulant for treatment, prophylaxis or otherwise. Therapy with heparin, low molecular weight heparin (LMWH), newer anti-coagulation agents such as direct factor Xa inhibitors, or fondaparinux is allowed

8. Patient is currently receiving or has received systemic corticosteroids \leq 2 weeks prior to starting study drug, or who have not fully recovered from side effects of such treatment.
 - a. The following uses of corticosteroids are permitted: single doses, topical applications (e.g., for rash), inhaled sprays (e.g., for obstructive airways diseases), eye drops or local injections (e.g., intra-articular).
9. Patient has impairment of gastrointestinal (GI) function or GI disease that may significantly alter the absorption of the study drugs (e.g., ulcerative diseases, uncontrolled nausea, vomiting, diarrhea, malabsorption syndrome, or small bowel resection).
10. Patient has any other concurrent severe and/or uncontrolled medical condition that would, in the investigator's judgment, cause unacceptable safety risks, contraindicate patient participation in the clinical study or compromise compliance with the protocol (e.g. chronic pancreatitis, chronic active hepatitis, active untreated or uncontrolled fungal, bacterial or viral infections, etc.).
11. Participation in a prior investigational study within 30 days prior to enrollment or within 5 half-lives of the investigational product, whichever is longer
12. Patient has had major surgery and/or radiotherapy within 14 days prior to receiving study drug or has not recovered from major side effects (tumor biopsy is not considered as major surgery).
13. Patient with a Child-Pugh score B or C.
14. Patient has not recovered from the acute effects of prior systemic therapy (until the toxicity resolves to either baseline or at least Grade 1) except for residual alopecia or peripheral neuropathy.
15. Patient has a history of non-compliance to medical regimen or inability to grant consent.
16. Sexually active males unless they use a condom during intercourse while taking the drug and for 21 days after stopping treatment and should not father a child in this period. A condom is required to be used also by vasectomized men in order to prevent delivery of the drug via seminal fluid.

3.3. Participation of Special Populations

A discussion of the inclusion, exclusion, representation and participation of women, minorities, children, HIV positive individuals and vulnerable populations is provided in [Section 17.6](#).

4. PARTICIPANT ENROLLMENT

NOTE: Sites must meet activation requirements prior to enrolling participants (See the COH Data Coordinating Center (DCC) Supplement).

4.1. Pre-Enrollment Informed Consent and Screening Procedures

Diagnostic or laboratory studies performed exclusively to determine eligibility will be done only after obtaining written informed consent. Studies or procedures that are performed for clinical indications (not exclusively to determine study eligibility) may be used for baseline values and/or to determine pre-eligibility, even if the studies were done before informed consent was obtained. The informed consent process is to be fully documented (see [Section 17.4](#)), and the prospective participant must receive a copy of the signed informed consent document.

4.2.2. Slot verification and reservation

Eligible participants are stratified based on age. Designated study staff should call the DCC to verify current slot availability, and to reserve a slot for a specific prospective subject. Slots can only be held for a limited time by an institution.

The DCC should be notified of cancellations of prospective participants holding slots as soon as possible.

4.2.3. Registration Process

To register a participant, the subsequent procedure is to be followed.

1. The participating site's data manager/coordinator/research nurse should contact the DCC via telephone or email to provide notification regarding the pending registration and communicate desired timeline of the registration, especially if it must be completed promptly to meet the registration window.
2. The data manager/coordinator/research nurse should then e-mail copies to [contact] of the following documents to the DCC:
 - o Registration Cover Sheet ([Appendix C](#))
 - o Completed Eligibility Criteria List (printed from [Section 3.0](#) of the protocol)

- Source documentation to support eligibility criteria**
- Signed informed consent document
- Signed HIPAA authorization form (if separate from the informed consent document)
- Signed subject's Bill of Rights (COH only)

**For COH participants, provide copies of source documentation only if not readily available as a finalized record in the COH Electronic Medical Record (EMR).

3. After having received all transferred documentation, the DCC will complete and review the documents to verify eligibility, working with the participating site as needed to resolve any missing required source elements. A subject failing to meet all protocol eligibility requirements will not be registered.
4. Once eligibility has been confirmed, DCC staff will register the participant by: assigning a subject accession number, register the subject on study centrally into MIDAS for non-COH participants (the COH CRC will directly accession into MIDAS), and enter the subject into the eCRF system, Medidata RAVE.
5. Once registration has been completed, DCC staff will send a Confirmation of Registration Form, including the participant study number to:
 - the site study team: site PI, treating physician, protocol nurse, CRC and pharmacy
 - the COH sponsor team designees

4.3. Screen Failures and Registered Participants Who Do Not begin Study Treatment

All sites should maintain a screening log of potential participants meeting age criteria who were considered for the study but did not meet eligibility criteria. The log should detail the reason for screen failure.

The DCC is to be notified of all participants who sign consent but do not meet eligibility criteria or do not initiate study treatment. For non-COH sites, the reason for screen failure will be documented in registration coversheet (see [Appendix C](#)) and submitted to the DCC.

4.4. Stratification

Participants will be stratified based on age. A minimum of 20 evaluable participants ≥ 75 years must be enrolled. The remaining 20 evaluable participants may be ≥ 70 to < 74 years OR ≥ 75 years.

5. TREATMENT PROGRAM

5.1. Treatment Overview

Participants will be administered protocol therapy consisting of ribociclib in combination with aromatase inhibitor in the outpatient setting.

Participants who end protocol therapy will undergo long-term follow-up ([Section 5.1](#)). Windows for all assessments and treatments are detailed in [Section 11.0](#).

5.2. Treatment Cycle Definition and Day Count

A cycle will be a fixed 28 (± 2) days in duration (Note: exceptions under certain circumstances are permitted; see [Section 6.2.1 \(8\)](#)).

The cycle day count and cycle count continue despite a hold in ribociclib administration due to toxicities (See [Section 6.2.1](#)) - i.e. a cycle may initiate even if ribociclib is being held.

Day 1 safety assessments must be reviewed prior to initiation of ribociclib during a new cycle.

Cycle 1 Day 1 is defined as the first day the participant initiates combined ribociclib and endocrine therapy regimen (See [Table 5.3](#)).

5.3. Treatment Plan and Agent Administration

Table 5.3: Treatment regimen

Agent	Starting Dose	Frequency of Administration	Route of Administration
Ribociclib	600 mg/ day	Once daily on Days 1-21 of each 28-day cycle	Orally
Aromatase inhibitor	Per package insert	Per treating investigator's discretion during each 28-day cycle	Per package insert

5.3.1. Ribociclib

Ribociclib should be taken at approximately the same time each day with food. Ribociclib tablets should be swallowed whole.

If applicable, ribociclib may be taken at the same time as endocrine therapy.

If a patient vomits or misses a dose, an additional dose should not be taken that day. The next prescribed dose should be taken at the usual time.

Management and dose modification associated with ribociclib adverse events are outlined in [Section 6.2](#). ribociclib doses missed for toxicity will not be made up during a cycle.

Participants will be supplied with a Pill Diary ([Appendix E](#)) to assess ribociclib compliance.

Ribociclib has been shown to prolong the QT interval in a concentration dependent manner, with mean increase in QTc interval being 22.9 ms (90% CI: 21.6-24.1). Therefore, ECG will be assessed prior to initiation of treatment and patients will only be eligible if QTcF values under <450 msec.

5.3.2. Aromatase inhibitor:

Participants will receive an aromatase inhibitor, according to the package insert and investigator discretion.

Modification in the dose of endocrine therapy due to unacceptable toxicity will occur per treating investigator's discretion.

The type of aromatase inhibitor may be switched at the treating investigator's discretion. Types of aromatase inhibitor includes letrozole, exemestane and anastrozole.

5.4. Duration of Protocol Therapy - Criteria for Ending Protocol Therapy

Participants will receive protocol therapy until one of the below criteria are met:

- Disease progression
- Participant is deemed intolerant to ribociclib because of toxicity, despite dose modification/ delay
- General or specific changes in the patient's condition which render the patient unacceptable for further treatment in the judgment of the investigator
- Withdrawal of consent for further protocol therapy by the participant (See [Section 17.5](#))

Once participants meet criteria for removal from protocol therapy, the participant should then proceed to End of Treatment and 30-Day-Post Last-Dose visits.

Documentation of the reason for discontinuing protocol therapy and the date effective should be made in the medical record and appropriate eCRF. **The COH DCC should be promptly notified of the change in participant status.**

5.5. Long-Term Follow-Up

All participants whose disease had not progressed at the time of end of protocol therapy will undergo **medical chart review for disease progression/response** information until disease progression or the initiation of a new therapy. Medical chart review should occur at least twice annually or as requested by the lead study team.

All participants will be followed for **survival information** by the site and/or by the lead study team designee. If performed by the lead study team, the following information will need to be transferred to the designee in a secure manner: the participant's first and last name, middle initial, social security number, date of birth, and gender. Methods for capturing survival status may include the Social Security Death Index and the National Death Index. Survival analysis will be conducted at least annually or as requested by the lead study team.

5.6. Criteria for Completion of Study Participation

Study participation may conclude when any of the following occur:

- Participant withdrawal (see [Section 17.5](#)).

- Participant is lost to follow-up. All attempts to contact the participant must be documented.
- At the discretion of the investigator for safety, behavioral or administrative reasons Documentation of the reason for discontinuing study participation and the date effective should be made in the medical record and appropriate eCRF. **The COH DCC should be promptly notified of the change in participant status.**

5.7. Supportive Care, Other Concomitant Therapy, Prohibited Medications

Patients should receive full supportive care during the study, including treatment with antibiotics, antiemetics, blood transfusions, antidiarrheals, and analgesics as appropriate, with the exception of prohibited drugs listed below per institutional policies.

5.7.1. Prohibited until end of protocol therapy

End of protocol therapy is when treatment with ribociclib will no longer continue.

- No other investigational therapy should be given to participants
- No anticancer agents other than the study medications administered as part of this study protocol should be given to participants. If such agents are required for a participant then the participant must first be withdrawn from the study.
- Co-medication that may interfere with study results; e.g. immuno-suppressive agents other than corticosteroids, such as systemic cyclosporine and tacrolimus are prohibited during the treatment phase of the study, unless discussed with principal investigator felt to be of low clinical risk to the participant.
- Use of herbal medications may have unknown interactions with the metabolism of the study agents, and therefore are prohibited from use during the treatment phase of the trial.
- Strong CYP3A inhibitors/inducers including St. John's Wort and Grapefruit. Refer to [Appendix B](#) for an extensive list.
- Drugs known to cause QT interval prolongation. Refer to [Appendix B](#) for an extensive list.
- Hormone replacement therapy, topical estrogens (including any intra-vaginal preparations), megestrol acetate and selective estrogen-receptor modulators (eg, raloxifene).

5.7.2. Use with caution

- Medications that are substrates of CYP3A4 with narrow therapeutic indices may need to be reduced when given concurrently with ribociclib.
- Steroids given for physiological replacement, as anti-emetics or inhaled as well as short course of oral/topical steroids given for allergic reactions or asthma flares.
- Prophylactic use of white blood cell growth factors with ribociclib is not recommended

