APPENDIX B: PROHIBITED MEDICATIONS / MEDICATIONS TO BE USED WITH CAUTION

List of prohibited medications during study drug treatment

Category	Drug Name
Strong CYP3A4/5 inhibitors	Atazanavir/ritonavir, boceprevir, clarithromycin, cobicistat, conivaptan, danoprevir/ritonavir, darunavir/ritonavir, elvitegravir/ritonavir, grapefruit juice, idelalisib, indinavir, indinavir/ritonavir, itraconazole, ketoconazole, lopinavir/ritonavir, mibepradil, nefazodone, neflunavir, ombitasvir/paritaprevir/dasabuvir/ritonavir (VIEKIRA PAK), posaconazole, ritonavir, saquinavir/ritonavir, telaprevir, telithromycin, tipranavir/ritonavir, troleandomycin/voriconazole
Strong CYP3A4/5 inducers	carbamazepine ³ , enzalutamide, lumacaftor, mitotane, phenobarbital, phenytoin ³ , rifabutin, rifampin (rifampicin) ³ , St. John's wort (hypericum perforatum) ^{2,3}
CYP3A4/5 substrates with NTI¹	Alfentanil, astemizole, cisapride, cyclosporine, diergotamine (dihydroergotamine), ergotamine, fentanyl, pimozide, quinidine, sirolimus, tacrolimus
Medications with a known risk for QT prolongation⁴	Amiodarone, anagrelide, arsenic trioxide, astemizole, azithromycin, chloroquine, chlorpromazine, cilostazol, ciprofloxacin, cisapride, citalopram, clarithromycin, disopyramide, dofetilide, domperidone, donepezil, dronedarone, droperidol, erythromycin, escitalopram, flecainide, fluconazole, gatifloxacine, grepafloxacin, halofantrine, haloperidol, ibutilide, levofloxacin, levomepromazine, levosulpiride, methadone, moxifloxacin, ondansetron, oxaliplatin, papaverine HCl (intra-coronary), pentamidine, pimozide, procainamide, propofol, quinidine, roxithromycin, sevoflurane, sotalol, sulpiride, sultopride, terlipressin, terodilane, thioridazine, vandetanib
Herbal preparations/ medications	Herbal preparations/medications known as strong inducers or inhibitors of CYP3A4/5 or those with a known risk of QT prolongation are prohibited throughout the study. These herbal medications include, but are not limited to: St. John's wort, Kava, ephedra (ma huang), gingko biloba, dehydroepiandrosterone (DHEA), yohimbe, saw palmetto, and ginseng. Patients should stop using these herbal medications 7 days prior to first dose of study drug.

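### Narrow-therapeutic-index CYP3A4/5 substrates are prohibited during treatment in Appendix B but listed for use with caution in Section 5.7.2

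*Combined protocol and SAP*

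**What the plan says.** Four places in the combined protocol and SAP deal with this drug class.

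- **Section 3.2, exclusion 7.** The stem reads "Patient is currently receiving any of the following medications and cannot be discontinued 7 days prior to starting study drug". Item 7b then names drugs "That have a narrow therapeutic window and are predominantly metabolized through CYP3A4/5". Item 7d names "Warfarin or other coumadin-derived anticoagulant for treatment, prophylaxis or otherwise" and goes on to list other anticoagulants that are allowed. The stem refers the reader to a Table 1.
- **Section 5.7.1 (prohibited until end of protocol therapy).** It does not name the narrow-index class. It covers two of the drugs as immunosuppressants: "such as systemic cyclosporine and tacrolimus are prohibited during the treatment phase of the study, unless discussed with principal investigator". It cites Appendix B for strong CYP3A inhibitors and inducers and for QT-prolonging drugs only.
- **Section 5.7.2 (use with caution).** "Medications that are substrates of CYP3A4 with narrow therapeutic indices may need to be reduced when given concurrently with ribociclib".
- **Appendix B.** Under the title "List of prohibited medications during study drug treatment", the row for CYP3A4/5 substrates with a narrow therapeutic index reads: "Alfentanil, astemizole, cisapride, cyclosporine, diergotamine (dihydroergotamine), ergotamine, fentanyl, pimozide, quinidine, sirolimus, tacrolimus". The row has no waiver.

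**The concern.** Section 5.7.2 presupposes the concurrent use that Appendix B forbids. An investigator whose patient needs one of these drugs in, say, cycle 3 gets opposite answers from the two places. The cross-references do not settle it, because nothing in Section 5.7 points to the Appendix B row for this class. Section 5.7 also allows analgesics as appropriate except for the prohibited drugs listed below it. Fentanyl is not named in that list, yet it is in Appendix B.

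At stake is consistent handling of a class that the protocol itself treats as sensitive enough to bar, across nine listed sites in a trial whose purpose is to describe tolerability.

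**Working it through.** No figure in the plan depends on this point, so there is nothing to recompute. The check sets the rules side by side, drug by drug.

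**Step 1. Status of the class.** Exclusion 7b and Appendix B agree: the drug must be stoppable before entry and is prohibited during treatment. Section 5.7.2 gives the class a different status during treatment.

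**Step 2. Status of each named drug.** The 11 drugs in the Appendix B row were compared with Section 5.7.1 and with the Appendix B row for known QT risk.

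| Drugs | Count | Section 5.7.1 | Appendix B | Result |
|---|---|---|---|---|
| Alfentanil, dihydroergotamine, ergotamine, fentanyl | 4 | No prohibition, so only 5.7.2 applies within Section 5.7 | Prohibited | Direct conflict |
| Cyclosporine, tacrolimus, and sirolimus if read as an immunosuppressant | 3 | Prohibited, with a principal-investigator waiver | Prohibited, no waiver | Differ by the waiver |
| Astemizole, cisapride, pimozide, quinidine | 4 | Prohibited as QT-prolonging drugs, citing Appendix B | Prohibited, in two rows | Agree |

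Check: 4 + 3 + 4 = 11. Cyclosporine and tacrolimus are named in Section 5.7.1. Sirolimus is not, and belongs in the second group only if the general reference to immunosuppressive agents is taken to include it.

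**Step 3. Whether another part of Appendix B resolves it.** The caution list in Appendix B has a row for sensitive CYP3A4/5 substrates. That is a different class with its own footnote definition, and none of the 11 drugs is in it. Section 5.7.2 names the narrow-index class, so this row does not reconcile the two texts.

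**Step 4. Warfarin.** It is named once, in exclusion 7d. It is absent from Sections 5.7.1, 5.7.2 and 6.2 and from both Appendix B lists. The number of named on-treatment rules is therefore 0. Whether the narrow-index class was meant to cover it cannot be settled: exclusion 7 lists it separately from 7b, and the Appendix B row omits it.

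**Step 5. Table 1.** The protocol's list of tables contains no Table 1.

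**The case against.** The strongest reply is that the practical conflict is small and that several larger claims do not follow. Most of this stands.

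- **All eleven drugs.** A reader might infer that all 11 are prohibited in one place and permitted in another. Step 2 shows otherwise: four conflict directly, three differ by a waiver, and four are prohibited in both places.
- **Eligibility.** A reader might infer that sites would differ on admitting a patient who uses a fentanyl patch. The documents do not support that. Exclusion 7b governs entry, and under Section 4.2.3 the coordinating center verifies eligibility and does not register a patient who fails a criterion. What remains open is starting or restarting such a drug on treatment.
- **Warfarin.** A reader might infer that the protocol permits warfarin from Day 2. Silence is not permission, and 7d names allowed alternatives. This is an omission, not a contradiction.
- **Severity of harm.** Appendix B footnote 1 links serious safety concerns to raised exposure caused by potent inhibitors. The documents do not class ribociclib as a potent CYP3A inhibitor, so the footnote cannot be cited as showing that ribociclib causes such harm. Nor does it reach warfarin, which is not in the row.
- **Primary endpoint.** A reader might infer that the primary rate would depend on which section each site follows. There is a route: Section 13.1.4 counts events at least possibly attributed to ribociclib, and Section 7.1.2.2 lets an event be rated possible even if a concomitant drug could explain it. The size cannot be derived. If the endpoint counts patients with at least one qualifying event, an extra event in a patient already counted changes nothing. In the ribociclib trial summarized in Section 2.4.1, grade 3-4 neutropenia alone was 59.3%. Taken as a rough guide, and noting that it was not restricted to attributed events, that leaves at most 100 - 59.3 = 40.7% of patients in whom such an event could be new.

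None of these replies removes the contradiction between Section 5.7.2 and Appendix B.

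**Conclusion.** The on-treatment rules contradict each other as written. The direct conflict covers four named drugs. For two further drugs, or three with sirolimus, a waiver exists in Section 5.7.1 but not in Appendix B. Section 5.7.2 also speaks of the class as a whole, so its wording conflicts with the Appendix B row beyond the named examples.

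The documents give no usage rate for these drugs, so any count of affected patients among the 40 would be a guess, and none is offered. No effect on the primary estimate is claimed. The case for acting is consistent and safe conduct at the sites.

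The conclusion rests on the text of Sections 3.2, 5.7, 5.7.1 and 5.7.2 and Appendix B. It assumes that pages absent from the public copy carry no further medication rule. Judging by the table of contents, those pages are title, enrollment, registration-coversheet and shipping material, so this is likely. The warfarin gap and the Table 1 pointer are secondary; the pointer alone is clerical.

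**What to change.** Reconcile Sections 5.7.1 and 5.7.2, Appendix B and exclusion 7b so that narrow-index CYP3A4/5 substrates have one status during treatment. Have Section 5.7 refer to the Appendix B row for this class. State whether the Section 5.7.1 exception ("unless discussed with principal investigator felt to be of low clinical risk to the participant") overrides Appendix B, and whether it extends to sirolimus. Which status is right is for the sponsor and its clinical pharmacology advisers.

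In the same amendment:

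- State the on-treatment status of warfarin and other coumadin-derived anticoagulants, including restarting after a stop made to meet exclusion 7d.
- Correct the Table 1 pointer in exclusion 7. Pointing to Appendix B would serve 7d only if warfarin is also addressed there.

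The cost is wording in one amendment and a notice to sites. No new data, visits or procedures are needed.
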